3.3.10 Compliance Definition for Clinical Outcome Assessments

Summary measures of compliance over time will be derived for the COAs. These will be based on the following:

- All items/questions completed
- At least meets minimum requirements for calculation of one subscale or a total score of the questionnaire (applicable to **CCI** only)
- At least meets minimum requirement for calculation of the **CCI** (applicable to **CCI**, **CCI** scale only)
- At least one question completed

For COAs with only one question (**CCI**), the category “Questionnaire completed” will be presented.

CCI compliance will be summarised for AM and PM of each visit. The participant will have complied if the **CCI** field of the diary is not missing.

The compliance for palatability will be summarised by item and week and based on the following:

- Expected number of participants
 - A participant is expected to complete Item 2 only if she/he responded ‘No’ at least once to Item 1.
 - A participant is expected to complete Item 3 only if she/he responded “No” at least once to Item 1 and or “Other” to Item 2, or having first responded “Yes” to Item 1.
- Expected number of entries
 - The expected number of diary entries for Items 1, 4, and 5 is; expected number of participants x 2 (number of daily assessments) x the number of days the participant is on treatment without transitioning to capsules in the first week of the Cycle 1 or Cycle 7 (until a maximum of 7 days).
 - The expected number of diary entries for Item 2 is: number of entries (Item 1 = “No”).

- The expected number of diary entries for Item 3 is: number of entries (Item 1 = “No” and Item 2 = “Other”) plus number of entries (Item 1 = “Yes”).
- Subjects with at least one item completed at least once (count and percentage)
 - Percentage will be calculated as the number of participants with item entry completed at least once divided by the expected number of participants in a week.
- Item completion rate (count and percentage)
 - Completion rate will be calculated as the number of actual completed item diary entries divided by the expected number of item diary entries in a cycle.

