4.2 Endpoint Analyses

This section covers details related to the endpoint analyses such as primary, secondary, and other endpoints including sensitivity and supportive analyses.

The CCI [REDACTED] and CCI [REDACTED] analyses will not form part of the clinical study report and will not be handled by the statistical and programming vendor. The CCI [REDACTED] and CCI [REDACTED] analyses will be analysed and presented separately from the main clinical study report. Thus, they are outside the scope of this SAP.

Statistical category	Endpoint	Population	Population level summary (analysis)	Details in section
To determine the PK of selumetinib after administration of the selumetinib granule formulation				
Primary	Selumetinib AUC0-12 derived after single dose administration	PK	Descriptive statistics	4.4
To assess the safety and tolerability of the selumetinib granule formulation				
Primary	AEs, AESIs and SAEs. Duration of exposure and treatment compliance percentage. Absolute values and changes from baseline in Laboratory assessments. Vital signs, ECG, ECHO, ophthalmologic assessment, Knee (or wrist) MRI/X ray, and performance status.	Safety	Descriptive statistics	4.6
To assess the palatability of the selumetinib granule formulation				
Secondary	Palatability will be assessed using the parent-reported observer palatability assessment.	Safety	Descriptive statistics	4.2.3
To further assess the PK of selumetinib and N-desmethyl selumetinib metabolite after administration of the selumetinib granule formulation				

Statistical category	Endpoint	Population	Population level summary (analysis)	Details in section
Secondary	Single and multiple dose plasma concentrations and PK parameters of selumetinib and N-desmethyl selumetinib (see Section 4.4 for list of parameters).	PK	Descriptive statistics	4.4
To evaluate the efficacy of the selumetinib granule formulation by assessment of ORR as determined by ICR per REiNS criteria				
Secondary	ORR Safety ORR estimate and	4.2.5	two-sided 95% CI based on the exact CCI	

To evaluate the efficacy of the selumetinib granule formulation by assessment of CCI [REDACTED] and CCI as determined by ICR per REiNS criteria				
Exploratory	CCI [REDACTED]	Participants who have a CCI [REDACTED] in safety	CCI [REDACTED] CCI [REDACTED] CCI [REDACTED] CCI [REDACTED]	4.2.6
Exploratory	CCI [REDACTED]	Safety	CCI [REDACTED] [REDACTED]	4.2.7
Exploratory	CCI [REDACTED]	Safety	CCI [REDACTED] CCI [REDACTED]	4.2.8

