4.2.3 Palatability

4.2.3.1 Definition

An assessment of palatability (the overall appreciation of the product in relation to its smell, taste, aftertaste, and texture) will be conducted using a parent-reported observer palatability assessment. It assesses the willingness to swallow and other observed behaviour on administration of an oral medication.

Assessments will be collected twice daily for Cycle 1 Week 1 and Cycle 7 Week 1. If the assessment cannot be done at Cycle 1 Week 1 and/or Cycle 7 Week 1, then it should be performed as soon as possible afterwards. The Cycle 1 Week 1 and Cycle 7 Week 1 assessments should not be completed if the participants are receiving selumetinib capsules or discontinue study intervention. Additional optional assessments of palatability can be performed for 7 days when a participant changes doses due to a change in BSA.

A copy of the palatability scale is provided in CSP Appendix J 6. The questions are separated in items as follows:

- Item 1: Did your child take their study medication this morning/evening? (Yes/No)
- Item 2: What was the reason for missing the dose? (Only if Item 1 = No)
- Item 3: Choose the response that best matches a description of what you observe of the child's willingness to swallow the study medication (if Item 1 = Yes or [if Item 1 = No and Item 2 = Other])
- Item 4: Was any behaviour observed when the study medication was given to this child that would be indicative of a negative response to the palatability of the study medication? (If Yes, three additional questions will be answered: 1. Did the child turn their head to reject intake of the medication? 2. Did the child twist their face or mouth in an expression of displeasure? 3. Did the child display any other negative behaviour?)
- Item 5: Were you able to prepare and dose the granules according to the Handling Instructions? (If No, one additional question will be answered: If no, please indicate which area/s you had difficulty in following?)

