4.2.3.2 Analysis of Palatability

Summaries for cumulative participant disposition and compliance over time (defined in Sections 3.3.9 and 3.3.10, respectively) by each scheduled visit week will be reported.

Derived Number of expected entries, Counts and percentages of completed entries will be summarised for items 1 to 3. Summaries by Cycle 1 Week 1, by Cycle 7 Week 1 and overall will be presented.

For item 2 besides of all responses, the combination of the responses “My child did not want to take the dose / My child could not swallow the medication (indicating palatability issues)” will be presented. For item 3 besides of all responses, the combination of the responses “Swallowed without problem / some resistance but did swallow” and “Spit out some/all medication / vomited up medication” will be presented.

For Items 1 to 3, the percentage distribution of completed entries over the number of expected entries at Cycle 1 Week 1 and Cycle 7 Week 1 will be visualised using a stacked Bar Chart combining all categories responses in the bar of each item, by summing up to 100%. The plot will be repeated separately for Cycle 1 Week 1 and for Cycle 7 Week 1, and overall.

All results will also be listed.

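### Palatability responses are summarised per diary entry, and no planned summary counts the children who had a palatability problem

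*SAP*

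**What the plan says.** The endpoint table in SAP 4.2 lists palatability as secondary, analysed descriptively on the safety set: "Palatability will be assessed using the parent-reported observer palatability assessment". SAP Table 1 places it at DCO1 and DCO2.

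SAP 4.2.3.1 sets the frequency: "Assessments will be collected twice daily for Cycle 1 Week 1 and Cycle 7 Week 1".

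SAP 4.2.3.2 makes the diary entry the unit of the response summary: "Counts and percentages of completed entries will be summarised for items 1 to 3". The tables are shown for each of the two weeks and overall. Two sets of grouped answers are added, also per entry: unwilling or unable to take the dose (Item 2), and swallowed versus spat out or vomited (Item 3). The stacked bars show "the percentage distribution of completed entries over the number of expected entries". All results are listed.

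SAP 3.3.10 fixes the denominators. For Items 1, 4 and 5 the expected entries are two per day times "the number of days the participant is on treatment without transitioning to capsules in the first week of the Cycle 1 or Cycle 7", to a maximum of seven days. Item 3 is expected only when the dose was taken, or was missed for a reason coded as other. Under SAP 3.3.9, nothing is expected once a child is off treatment or on capsules.

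The child-level counts in SAP 3.3.10 are the number of children expected for an item and the number who completed it at least once.

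**The concern.** The granules were developed for children who are too small for capsules or may be unable to swallow them (protocol 2.1). For such a product, a reader of the palatability result will want to know how many children accepted it. An entry-level percentage answers a different question: what share of recorded administrations went well. The two agree only if problems are spread evenly over children and every child contributes the same number of entries. Neither is assured here, and the second is ruled out by the SAP's own denominator rule whenever a child stops or changes formulation.

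The SAP treats similar data differently elsewhere. Two other seven-day diaries are reduced to a weekly average per child (SAP 4.2.11.2 and 4.2.12.2), and adverse events are counted by participant (SAP 4.6.2.2). No reason is given for handling palatability responses otherwise.

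At stake is what can be concluded from a secondary endpoint. The planned summaries cannot separate a small group of children who persistently reject the product from a mild, occasional problem in most children.

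**Working it through.** The plan states no target, precision or sample size for palatability, so there is no figure to reproduce. The check applies the SAP's denominator rule.

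**Inputs**
- Expected entries per child per week: 2 × days on granules, at most 2 × 7 = 14; at most 28 over both weeks (SAP 3.3.10, 4.2.3.1).
- Expected entries after stopping or moving to capsules: 0 (SAP 3.3.9).
- Number of children N: redacted. Values of 20, 30 and 40 are assumed.

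**1. How many children does an entry percentage imply?** With E = 14N expected entries and B problem entries, the number of affected children lies between B/14 (rounded up) and the smaller of N and B. Take B = 10% of E:

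| N (assumed) | E | B | Fewest children | Most children |
|---|---|---|---|---|
| 20 | 280 | 28 | 2 (10%) | 20 (100%) |
| 30 | 420 | 42 | 3 (10%) | 30 (100%) |
| 40 | 560 | 56 | 4 (10%) | 40 (100%) |

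These are bounds, not predictions.

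Only one dose is given on Cycle 1 Day 1 (protocol 6.1.1), so a child who takes every dose that week has 1 + 2 × 6 = 13 doses on which Item 3 can be answered, against 14 expected entries. Using 13 changes nothing of substance: for N = 30, 39/390 = 10% still fits 3 children (3 × 13 = 39) or all 30.

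**2. Weight of a child who leaves early.** A child who stops after Day 2 has 2 × 2 = 4 expected entries. That is 4/14 = 29% of a full child in Cycle 1 Week 1, 4/28 = 14% overall, and 0 in Cycle 7 Week 1. A child who completes the first week but is off granules by Cycle 7 has 14/28 = 50% of a full child's overall weight.

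**3. What Item 3 leaves out.** A dose the child would not take or could not swallow is answered No at Item 1 and given a reason at Item 2. The form then skips Item 3 (protocol Appendix J 6), and SAP 3.3.10 does not expect it. A child who refuses every dose therefore adds nothing to either part of the spat-out/vomited percentage.

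**4. Illustration.** Suppose 3 children spit out every dose and stop after Day 2, and all the others stay on granules with no problem. Problem entries are 3 × 4 = 12. The denominators are 14(N − 3) + 12 for Cycle 1 Week 1 and 28(N − 3) + 12 overall.

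| N (assumed) | Children affected | Entries, Cycle 1 Week 1 | Entries, Cycle 7 Week 1 | Entries, overall |
|---|---|---|---|---|
| 20 | 3/20 = 15.0% | 12/250 = 4.8% | 0% | 12/488 = 2.5% |
| 30 | 3/30 = 10.0% | 12/390 = 3.1% | 0% | 12/768 = 1.6% |
| 40 | 3/40 = 7.5% | 12/530 = 2.3% | 0% | 12/1048 = 1.1% |

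Counting actual doses instead (3 per early stopper, 13 per other child), the Cycle 1 Week 1 figure for N = 30 is 9/(13 × 27 + 9) = 9/360 = 2.5%.

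**The case against.** The instrument is completed at each administration, so the share of doses swallowed is a legitimate descriptive quantity. The SAP nowhere presents it as the share of children who accept the product. No hypothesis is tested (protocol 9.1) and no confidence interval is planned for palatability, so within-child correlation invalidates no standard error. All of this stands: the point concerns what the summaries can show, not an invalid inference.

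A reader might also infer stronger things that the documents do not support:

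- **That the endpoint is reported only as percentages.** Expected numbers and counts of entries are also planned, with each week shown separately.
- **That the number of affected children cannot be known.** Every result is listed, so it could be counted by hand. What is missing is a pre-specified summary, not the data.
- **That completion is the only child-level information.** The Item 2 expected-participant rule gives the number of children with any missed dose, but it mixes refusal with forgetting or an instruction to skip. Disposition, reasons for stopping treatment and adverse events, including choking and retching, are also per child. None of these says how many children refused, spat out or vomited a dose.
- **That the result is biased towards good palatability.** A child who refuses doses but stays on granules keeps full weight in Item 1. The planned move to capsules is prompted by body surface area, not taste, and nothing shows that children stop for taste in the first week. The separate Cycle 7 table, read beside disposition, makes attrition visible. The illustration shows that dilution can happen, not that it will.

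**Conclusion.** The point holds as a gap in the planned summaries. Palatability responses are tabulated and plotted per entry, no child-level summary of responses is specified, and the weight of each child depends on time on granules. Under the SAP's rule, an entry rate of 10% in a full week is compatible with anything from 10% to 100% of children affected at each assumed N (20, 30, 40). A child stopping after Day 2 carries 29% of full weight in Cycle 1 Week 1 and none in Cycle 7 Week 1. The weights follow from the SAP alone. The percentages in the illustration rest on an assumed N and an invented pattern of events. No direction of bias is established. The primary endpoints are unaffected, but the change is worth making because it alters what a secondary endpoint can show.

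**What to change.** Add one table to SAP 4.2.3.2 with the child as the unit, separately for Cycle 1 Week 1 and Cycle 7 Week 1:

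- The number and percentage of children with at least one dose refused, not swallowed, spat out or vomited, combining the relevant Item 2 and Item 3 answers. Keep children who stop early in the Cycle 1 denominator. In Cycle 7, state how many children remain on granules.
- The median (min-max) across children of the per-child percentage of doses swallowed. State how the Cycle 1 Day 1 evening slot, when no dose is scheduled, and doses forgotten or skipped on instruction enter the denominator.

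Keep the entry-level tables and bar chart as supportive. Dropping the pooled overall summary, or adding a category for children with problems at half or more of their doses, is optional.

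The cost is a short SAP revision and one table from data already collected. No new data, visits or protocol change are needed.

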4.2.4 Secondary Pharmacokinetic Endpoint

The definition, derivation, and analysis of all PK parameters are described in Section 4.4.

4.2.5 Secondary Efficacy Endpoint Objective Response Rate

4.2.5.1 Derivation of REiNS Tumour Response

For all participants, the REiNS tumour response data will be used to determine each participant's visit response according to the REiNS criteria. Tumour assessments will be measured by volumetric MRI. Baseline radiological tumour assessments are to be performed in the 28-day screening period. Unless clinically indicated otherwise, tumour assessments of the target and non-target PN (if relevant) will be obtained at screening and every 4 cycles (16 ± 1 weeks) relative to the date of first dose for the first 13 cycles and subsequently every 6 cycles (24 ± 1 weeks). The MRI data for participants who discontinue selumetinib prior to Cycle 25 will be collected if a suitable MRI is performed as standard of care until the time when they would have completed 25 cycles of treatment or they commence an alternative systemic NF1-PN treatment, whichever is the earliest. Volumetric MRI assessment will be performed by an AstraZeneca-appointed imaging CRO according to the REiNS criteria. A double read of all MRI scans will be performed. The ICR reviewers will be blinded to cohort and dose schema. Further details of the ICR will be documented in the IRC.

All volumetric MRI scans for all participants (including those at unscheduled visits or outside visit windows) will be collected on an ongoing basis and sent to an AstraZeneca-appointed imaging CRO for central analysis. The investigator will select the target PN and non-target PN (if relevant) based on the results of the Screening PN assessments. The details about target PN location and non-target PN location (if relevant) will also be collected and sent to the imaging CRO to ensure that the independent reviewer also follows the most clinically relevant PN. The imaging CRO will determine the tumour measurements of the target PN and non-target PN.

To determine the level of response, the average over the two assessed PN volumes from the double read will be derived, and follow-up scans will be compared to the baseline scan or the scan at the time of best response after documenting a PR for the same PN. Using the REiNS criteria, a change in volume of 20% is used to indicate an increase or decrease of

PN volume. For all participants, the target PN (see Section 4.2.5.2) and non-target PN (see Section 4.2.5.3), if applicable, will be assessed and both given a response (see [Table 5](#) and [Table 6](#)), and any new PNs will be recorded. At each visit, participants will be programmatically assigned an overall REiNS visit response of CR, PR, SD, or progressive disease (PD) using the information from target PNs, non-target PNs, and new PNs and depending on the status of their disease compared with baseline and previous assessments (see [Table 7](#)). If a participant has a PN assessment that cannot be evaluated, then the participant will be assigned a visit response of NE.

4.2.5.2 Target PN

The target PN is selected at screening. The target PN will be defined as the most clinically relevant PN (signs/symptoms/complications that have the most impact on the participant in the opinion of the Investigator) that is measurable by volumetric MRI analysis. If there is a second PN that is also considered clinically relevant, this may be identified as a non-target PN at baseline; only one non-target PN can be selected. Both target and non-target PNs must be symptomatic, measurable, and inoperable.

The target PN visit response will be derived as per [Table 5](#) using the average over both baseline PN volume assessments and the average over both visit PN volume assessments from ICR. [Table 5](#) is based on the recommendations from [Dombi et al 2013](#).

Table 5 Target PN Visit Responses (REiNS)

Visit responses	Description
Complete response (CR)	Disappearance of the target PN.
Partial response (PR)	Decrease in the volume of the target PN by 20% or more compared to baseline.
Progressive disease (PD)	Increase in the volume of the target PN by 20% or more compared to baseline or the time of best response after documenting a PR.
Stable disease (SD)	Insufficient volume change to qualify for either PR or PD (a < 20% increase or < 20% decrease in the volume of the target PN).
Not evaluable (NE)	Data unavailable for target PN assessment.

PN, plexiform neurofibromas; REiNS, Response Evaluation in Neurofibromatosis and Schwannomatosis.

cCR and cPR will be derived as CR/PR achieved on a consecutive scan within 3 to 6 months (\pm 1 week) with no missed or non-evaluable visits as per assessment schedule.

4.2.5.3 Non-Target PN and New PN

Only one non-target PN may be selected. Non-target PN must also be clinically relevant and measurable by volumetric MRI analysis. The target PN must also be symptomatic,

measurable, and inoperable. This section provides the definitions of the criteria used to determine and record a response for the non-target PN at each MRI assessment.

Non-target response will be derived using the PN volume over both ICR assessments as per [Table 6](#):

Table 6 Non-Target PN Visit Responses (REiNS)

Visit responses	Description
Progressive disease (PD)	Unequivocal progression of an existing non-target PN. In this study, unequivocal progression is defined as an increase in the volume of the non-target PN by 20% or more compared to baseline.
Non-progressive disease (non-PD)	Insufficient volume change to qualify for PD.
Not applicable (NA)	No non-target PN recorded at baseline.
Not evaluable (NE)	Data unavailable for non-target PN assessment.

PN, plexiform neurofibromas; REiNS, Response Evaluation in Neurofibromatosis and Schwannomatosis.

[Table 6](#) is based on the recommendations from [Dombi et al 2013](#).

Details of any new PNs will also be recorded in the CRF with the date of the first scan that revealed the new PN(s). The appearance of a new PN (with the exception of new discrete subcutaneous neurofibromas) that is unequivocally and completely distinct and separate from the target PN and the non-target PN, if applicable, or unequivocal progression of an existing non-target PN also qualifies for PD. The new PN must be confirmed by scans with PN details recorded in the CRF. Once a new PN has been identified, at subsequent time points, it will be classified as either absent, present, or NE (in the case where image quality issues prevent a full assessment of the previously identified new PN). For new PNs assessed by ICR, if during the double read both reviewers disagree, a third radiologist will perform adjudication. The assessment of the adjudicator will be used to define the overall visit response as described in the next section. Further details on the adjudication process can be found in the IRC.

4.2.5.4 Overall Visit Response

[Table 7](#) defines how the previously defined target PN and non-target PN visit responses will be combined with new PN information to give an overall visit response.

Table 7 Overall Visit Responses

Target PN	Non-target PN	New PN	Overall visit response
CR	Non-PD or NE or NA	No or NE	CR
PR	Non-PD or NE or NA	No or NE	PR
SD	Non-PD or NE or NA	No or NE	SD
PD	Any	Any	PD
NE	Non-PD or NE or NA	No or NE	NE
Any	Any	Yes	PD
Any	PD	Any	PD

CR, complete response; NA, not applicable; NE, not evaluable; PD, progressive disease; PN, plexiform neurofibroma; PR, partial response; SD, stable disease.

The overall visit response will be derived programmatically based on the derived target PN and non-target PN responses as well as the adjudicated new PN response as described in the previous sections. In addition, the ICR will provide two overall visit responses, one response for each reviewer of the double read. The ICR and investigator visit response will only be listed in source data listings. The handling of **CCI** in the ICR data can be found in the IRC.

